9.4 STATISTICAL ANALYSES

9.4.1 GENERAL APPROACH

For descriptive statistics, categorical variables will be presented as frequency counts and percentages. Continuous variables will be presented as means and standard deviations. If on visual inspection of q-q plots, distributions deviate significantly from normality continuous variables will also present median and interquartile range.

Where needed, inferential statistics will be generated using Chi-square tests, Fisher's exact tests, or t-tests as appropriate. If outcome variable distributions deviate significantly from normality then comparisons will be made using the Mann-Whitney U test .

9.4.2 MAIN ANALYSES TO ADDRESS AIM 1

Analyses to assess the feasibility of participant recruitment, retention, and adherence to interventions will use data obtained from study visit and randomization logs, intervention class attendance logs, and home intervention practice logs, primarily during the baseline and 8-week intervention period.

Feasibility of recruitment will be assessed by examining the proportion of participants who attend a Screening Visit who go on to be randomized ("Percentage of screenees who are eventually randomized").

Feasibility of participant retention during the intervention phase of the research will be assessed by examining the proportion of randomized participants in each intervention

arm who drop out before the 8-week visit ("Percentage of randomized participants who drop out by 8 weeks, by intervention arm").

Feasibility of promoting participant adherence to group intervention classes will be assessed by examining the percentage of non-dropout participants in each intervention arm who complete at least 75% of recommended group classes during the 8-week intervention period ("Percentage of non-drop-outs completing at least 75% of intervention classes over 8 weeks, by intervention arm").

Feasibility of promoting adherence to home intervention practice will be assessed by examining the percentage of non-dropout participants in each arm who complete at least 75% of recommended home practice hours during the 8-week intervention period ("Percentage of non-drop-outs completing at least 75% of home intervention practice over 8 weeks, by intervention arm").

For these aim 1 outcomes, the investigative team has set benchmarks of randomizing at least 50% of women who undergo screening visits. Participant drop-out rates of <15%, 15-25%, and >25% will be interpreted as indicating optimal, acceptable, and inadequate retention, respectively. Among non-dropouts, completion of >85%, 75-85%, and <75% of group classes and home practice hours will be considered to indicate optimal, acceptable, and inadequate adherence, respectively.

Although the main analyses to assess the feasibility of recruitment, retention, and adherence will rely on descriptive statistics, the investigative team may generate 95% confidence intervals (CIs) to explore the precision of these performance estimates if this is deemed useful to guide planning for a future randomized trial.

9.4.3 MAIN ANALYSES TO ADDRESS AIM 2

Analyses to assess the feasibility of teaching participants to practice their assigned interventions will focus on data obtained from a) participant questionnaires assessing their confidence in performing yoga or physical conditioning techniques according to protocol (i.e., self-efficacy in performing postures/exercises), and b) expert consultants' observations of participants' competence in performing these techniques (i.e., observed competence in performing postures/exercises). Participants will rate their self-confidence in performing each posture/exercise on a 5-point Likert scale (5-extremely, 4-very, 3-moderately, 2-somewhat, and 1-not at all confident). Expert consultants will observe and rate participants' success in performing each posture/exercise on a 5-point Likert scale (5-extremely, 4-very, 3-moderately, 2-somewhat, and 1-not at all confident).

Using data from the 8-week yoga posture self-efficacy questionnaires, the investigators will examine the percentage of participants completing the yoga intervention program who demonstrate at least moderate self-efficacy in performing postures, based on an average posture self-confidence/self-efficacy rating of 3 or higher ("Percentage of participants with at least moderate self-efficacy in performing yoga postures at 8 weeks").

Using data from expert yoga consultants' 8-week evaluations of participants, the investigators will examine the percentage of participants completing the yoga intervention program who are rated by the study yoga expert consultant as being at least "moderately" successful in performing core yoga postures at 8 weeks, based on an average observed posture competency rating of 3 or higher ("Percentage of participants rated as being at least moderately competent in performing yoga postures at 8 weeks").

For equipoise, similar analyses will be conducted for the physical conditioning group. Analyses will examine the percentage of participants completing the physical conditioning intervention program who indicate that they are at least "moderately" confident that they can perform core exercises at 8 weeks ("Percentage of participants with at least moderate self-efficacy in performing physical conditioning exercises at 8 weeks"), as well as the percentage of participants who are rated by the physical therapy expert consultant as being at least "moderately" successful in performing core exercises at 8 weeks ("Percentage of participants rated as being at least moderately competent at performing physical conditioning exercises at 8 weeks").

The investigators anticipate that over 75% of participants who complete the 8-week intervention programs will be at least "moderately" confident in performing postures or exercises by 8 weeks. Additionally, investigators expect that over 75% of participants completing intervention programs will be rated by an expert consultant as being at least "moderately" successful in performing study-specific postures or exercises by 8 weeks.

Although the primary analyses to assess the feasibility of teaching participants to perform study-specific intervention techniques will rely on descriptive statistics, the investigative team may generate 95% CIs to explore the precision of these estimates if this is deemed useful to guide planning for a future randomized trial.

9.4.4 MAIN ANALYSES TO ADDRESS AIM 3

Analyses to assess the completeness, quality, and distribution of data from pain-related outcome measures will focus on participants' pain severity/intensity, interference, and impact measures after 8 weeks of intervention training.

Among participants completing the 8-week intervention programs, the investigative team will examine the percentage who complete 7-day pain severity/intensity measures 8 weeks, either within or outside of recommended time windows ("Percentage of expected pain logs returned at 8 weeks"). The investigators will also examine the percentage of participants who complete pain interference questionnaires at 8 weeks ("Percentage of expected pain interference questionnaires returned at 8 weeks") and pelvic pain impact measures at 8 weeks ("Percentage of expected pelvic pain impact measures returned at 8 weeks").

The investigative team anticipates that over 90% of pain severity/intensity, interference, and impact measures anticipated at 8 weeks will be completed and returned. Additionally, the investigators anticipate that over 75% of these measures will be completed and returned within recommended time windows.

If rates of return of the above outcome measures at 8 weeks are adequate, the investigators will also examine the mean (and/or median) and standard deviation (and/or interquartile range) of change in pain severity/intensity, interference, and impact scores over 8 weeks. This may guide future efforts to identify well-behaved and relatively precise pain-related outcome measures for use as primary and secondary efficacy outcomes in a future full-scale efficacy trial.

Analyses will focus on the combined sample of participants reaching the 8-week timepoint, although further analyses may be performed to explore differences between intervention arms if the completeness or quality of outcomes data at 8 weeks is lower than expected. Additionally, investigators may generate 95% CIs to explore the precision of estimates if deemed useful to guide future trial planning.

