6.3 RANDOMIZATION AND BLINDING

Eligible women will be randomized in a 1:1 ratio to the therapeutic yoga or physical conditioning interventions, with stratification by study site. The randomization scheme will be generated by a computer algorithm using randomly permuted blocks of sizes of 2 and 4. To avoid manipulation of randomization, a statistician/analyst who is not otherwise involved in the study will prepare the randomization scheme.

When a participant is found to be eligible and willing to be randomized at the Baseline Visit, the coordinator will confirm appropriateness for randomization on the randomization assignment form in the Medrio electronic data capture system. The system will provide a randomization number corresponding to the participant's intervention assignment, consistent with the randomization scheme. Sequential randomization numbers will provide a check on the validity of randomization, and the system will be configured to prevent reversal or manipulation of randomization.

Although there is no effective way to completely blind participants in this trial to their intervention assignment, study procedures will preserve the blinding of investigators and staff involved in abstracting or analyzing outcomes. Only study personnel who are directly responsible for randomizing participants, administering interventions, or promoting adherence to interventions will be aware of intervention assignment. All personnel involved in abstracting, assessing, or analyzing pain-related outcomes will remain blinded until all participants have completed the final visit, trial data are edited and cleaned, and the dataset is locked.

The Medrio electronic data capture system will be programmed to hide information about intervention assignment from study investigators or staff who are required to remain blinded. Only study personnel who are required to remain unblinded will be given user rights in the Medrio system that allow them to view the intervention assignments for individual participants.

To minimize differential expectations of success between groups, participants will be told that they are participating in a study of two types of low-impact physical activity programs and that the investigators do not know which intervention is more effective for the management of chronic pelvic pain (which is true). While awareness of group

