Within the yoga intervention arm, additional analyses may be conducted to examine participants' self-efficacy and observed competence in performing each individual yoga posture, to identify specific components of the yoga program that may post special challenges for the target population. Within the physical conditioning intervention arm, similar additional analyses may be conducted to examine participant's self-efficacy and observed competence in performing each physical conditioning exercise. These analyses will focus on 8-week data, although additional exploratory analyses may examine participants' self-efficacy and observed competence in performing intervention techniques mid-way through the intervention programs at 4 weeks.

C) Additional analyses to examine the completeness/quality of follow-up outcomes data:

Additional analyses may be performed to assess the completeness and quality of data obtained from pain logs and pain-related outcome questionnaires at the 8-week post-intervention timepoint. This includes the percentage of completed 7-day pain severity/intensity, interference, and impact measures returned at the 8-week post-intervention timepoint.

Additional analyses may examine the percentage of other expected pain-related outcome measures that are returned at 8 weeks or 8-weeks post-intervention. These include pain self-efficacy or fear-avoidance questionnaires, anxiety and depression symptom questionnaires, and sleep disturbance questionnaires. For all of the above, analyses will focus on the combined available sample of participants at the relevant timepoint, although further exploratory group-specific analyses may also be performed.

The study team may also examine the distribution of data from all of the above pain-related outcome measures at baseline, 8 weeks, and 8 weeks post-intervention, and calculate their standard deviations (SDs) and within-subject and within-site intraclass correlations (ICCs). These exploratory analyses may alert the investigative team to the need for transformation and ceiling/floor effects as well as guide decisions about the inclusion of measures in a future full-scale trial.

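### The SD of 8-week pain change in Section 9.4.4 should be pooled within arms, because the combined-sample SD also contains any difference between the arms

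*Combined protocol and SAP*

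**What the plan says.** Section 9.4.4 (Aim 3) provides that, if return rates at 8 weeks are adequate, the team will examine the mean or median and the "standard deviation (and/or interquartile range) of change in pain severity/intensity, interference, and impact scores over 8 weeks". The result may help to "identify well-behaved and relatively precise pain-related outcome measures for use as primary and secondary efficacy outcomes" in a full-scale trial. The section does not define precision or give a rule for ranking measures.

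On the sample it says: "Analyses will focus on the combined sample of participants reaching the 8-week timepoint". By-arm work is optional there and depends on the data falling short of expectation: "further analyses may be performed to explore differences between intervention arms if the completeness or quality of outcomes data at 8 weeks is lower".

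Section 9.4.6 C, on completeness of the other measures and of the post-intervention data, says that "analyses will focus on the combined available sample of participants at the relevant timepoint", and adds "although further exploratory group-specific analyses may also be performed". That option has no trigger, but its content is not specified. The next paragraph allows SDs and intraclass correlations at baseline, 8 weeks and 8 weeks post-intervention. The correlations are by subject and by site, with no term for arm.

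On allocation, Section 6.3 says: "Eligible women will be randomized in a 1:1 ratio to the therapeutic yoga or physical conditioning interventions". Section 4.2 expects the later trial to have the same two-arm design.

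**The concern.** A two-arm efficacy trial compares arm means, so the precision of an outcome in that trial depends on how much women vary within an arm. The SD of all women together also contains the distance between the two arm means. The combined mean is likewise an average of yoga and control change, which describes neither arm.

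The excess differs from measure to measure: it is nil where the arms do not differ and grows with the arm difference. If measures are compared on SD, the comparison leans slightly against those that separate the arms. The condition for by-arm analysis in Section 9.4.4 does not address this, because data can be complete and of good quality while the arms differ.

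**Working it through.** **The plan's own precision figure.** Section 9.2 gives half-widths of 95% intervals for continuous measures of more than 0.30 SD overall and more than 0.45 SD within arms. These reproduce: 1.96/sqrt(36) = 0.327 and 1.96/sqrt(18) = 0.462. The plan states no SD of change and no effect size, so the rest uses assumed values.

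**Inputs.** Allocation 1:1 (Section 6.3); 36 women (Section 9.2); about 31 to 27 left at the 15% to 25% drop-out in the Section 9.4.2 benchmarks (36 × 0.85 = 30.6; 36 × 0.75 = 27). Assumed: equal within-arm SDs s, and a true arm difference of d × s with d from 0.3 to 1.0.

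**Step 1, size of the excess.** With half the women in each arm, each arm mean lies d·s/2 from the overall mean, so

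combined variance = s² + (d·s)²/4, and combined SD / within-arm SD = sqrt(1 + d²/4).

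| Assumed d | 1 + d²/4 | SD ratio | Excess |
|---|---|---|---|
| 0.3 | 1.0225 | 1.011 | 1.1% |
| 0.5 | 1.0625 | 1.031 | 3.1% |
| 0.8 | 1.1600 | 1.077 | 7.7% |
| 1.0 | 1.2500 | 1.118 | 11.8% |

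**Step 2, against sampling error.** The relative standard error of an SD is about 1/sqrt(2(n − 1)): 1/sqrt(70) = 12.0% at n = 36, 13.1% at n = 30 and 13.9% at n = 27. The bias is well below this at d = 0.3 to 0.5 and about equal to it at d = 1.0.

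**Step 3, effect on a comparison of two measures.** Take two measures with equal within-arm SDs, one responsive and one not. In 20,000 simulated trials per setting (n = 36 and 30; correlation between measures 0, 0.5 and 0.7), the responsive measure had the larger combined SD in:

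- 53–54% of trials at d = 0.3
- 57–60% at d = 0.5
- 66–72% at d = 0.8
- 74–81% at d = 1.0

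With the SD pooled within arms it was about 50% throughout.

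**Step 4, when the expected order reverses.** The responsive measure has the smaller expected combined SD if its within-arm SD is below 1/sqrt(1 + d²/4) of the other's: 0.970 at d = 0.5 and 0.894 at d = 1.0. The bias therefore reverses the expected order only if the responsive measure's within-arm SD is lower by no more than 3.0% or 10.6% respectively.

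**Step 5, in a single data set.** The combined SD exceeds the pooled within-arm SD only when the observed two-sample |t| is above 1. At n = 36 the noncentrality is d·sqrt(36)/2, that is 0.9 at d = 0.3 and 1.5 at d = 0.5, and |t| falls below 1 in about 51% and 30% of trials. The excess in Step 1 is thus an expectation, not something every data set will show.

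**The case against.** The strongest reply is that this matters little. The trial is a 36-woman feasibility study with no efficacy hypothesis, its primary composite outcome is unaffected, and the comparator is an active, time-matched programme, so the documents give no ground for a large d. At d = 0.3 to 0.5 the excess is 1% to 3%, far inside sampling error. All of that stands. What remains is that sampling error favours no measure systematically, whereas this bias leans against responsive ones in expectation and can be removed at almost no cost.

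A reader might go further in three ways that the documents do not support.

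- *That the measures responding most to yoga will look the least precise.* Steps 3 and 4 show a slight lean at moderate effects, and only when within-arm SDs are close. It also presumes ranking on SD alone, on a common scale, which the plan does not say. If precision were read as mean change over SD, the lean would go the other way: with an assumed control change of 0.3 SD, the combined ratio is 0.30 at d = 0 and (0.3 + 0.25)/1.031 = 0.53 at d = 0.5. That ratio would still mix change common to both arms with the arm difference.
- *That the later trial will be oversized.* Neither section says these SDs will set its sample size. Such a use would err on the safe side: at d = 0.5, with an assumed two-sided 5% level and 80% power, 67 instead of 63 per arm, giving 82.5% power.
- *That by-arm analysis is ruled out unless data quality is poor.* Section 9.4.6 C leaves an exploratory group-specific option open without a trigger. It names no within-arm SD of change, so it does not close the gap.

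Pooling might also be defended as protecting blinding or avoiding an efficacy reading. A pooled within-arm SD reveals no arm difference and can be computed with masked arm labels. Section 6.3 in any case lifts blinding once the data are locked.

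**Conclusion.** The point holds, as a minor one. Section 9.4.4 directs the SD of change to the combined sample, for a purpose that calls for the within-arm SD, and no section specifies the latter. In expectation the combined SD is too large by about 1% at d = 0.3, 3% at d = 0.5, 8% at d = 0.8 and 12% at d = 1.0. These figures rest on 1:1 arms, equal within-arm SDs and assumed values of d. The consequence is a slight disadvantage for more responsive measures when within-arm SDs are similar and measures are compared on SD. It is not a distortion that would dominate the choice of outcome. The case for changing the text is that the better statistic is available from the same data at negligible cost.

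**What to change.** Amend Section 9.4.4 as follows.

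- For each pain measure, report the SD of 8-week change pooled within arms, that is, the residual SD from a linear model with arm as the only factor.
- Show mean and SD of change by arm descriptively, with no efficacy test.
- Base the comparison of precision between measures on the pooled within-arm SD.
- Keep the combined sample for return and completion rates.

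The cost is one degree of freedom (34 instead of 35 with all 36 women), a sentence or two of analysis text and one line of code. No new data are needed.

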9.4.5 PRIMARY COMPOSITE FEASIBILITY OUTCOME

Although each of the above feasibility analyses will be important in planning for a future full-scale efficacy trial, the investigative team has also designated a single composite feasibility outcome that incorporates multiple of the above outcomes. This is the cumulative number of participants from all three planned intervention waves who:

- a) are randomized to one of the two intervention groups (yoga or physical conditioning),
- b) do not drop out of the study before the end of their assigned 8-week intervention program,
- c) attend at least 75% of their recommended group intervention classes over 8 weeks,
- d) report at least moderate self-efficacy (on average) in performing intervention techniques, and
- e) provide 7-day pain severity/intensity, impact, and interference data at 8 weeks.

The investigative team has set a benchmark of enrolling and following at least 24 women (or two-thirds of the randomization target of 36 women) who meet all of the above criteria by the end of three planned intervention waves of this feasibility trial. If this benchmark is not met, the study team will re-consider the advisability of proceeding with a full-scale trial that uses the same approach to recruitment and retention, delivering the study interventions, and collecting pain outcomes data.

9.4.6 ADDITIONAL ANALYSES

A) Additional analyses to assess the feasibility of recruitment, retention, and adherence:

Additional analyses will examine the number of initial inquiries, screening visits, and randomized participants generated by different types of recruitment methods in order to guide refinement of recruitment strategies. To assess the effects of study eligibility criteria on the feasibility of recruitment, the investigative team will tabulate the major reasons why screeners are found to be ineligible in the screening phase of the study.

To assess the feasibility of participant retention during the post-intervention phase of the study, the investigative team will examine the proportion of participants completing each intervention program who subsequently drop out of the study or are lost to follow-up by the 8-week post-intervention visit.

To examine the feasibility of promoting continued adherence to intervention practice after the end of the intervention programs, investigators will examine the proportion of participants completing the post-intervention follow-up phase of the study who also complete at least 75% of recommended home practice hours during this 8 week post-intervention period.

If participant retention is poor, the investigative team may conduct additional exploratory pooled logistic regression analyses to try to identify participant characteristics associated with drop-out by 8 weeks or 8 weeks post-intervention. Similarly, if adherence to group intervention classes or home practice is lower than expected, the investigative team may explore simple linear, logistic, and/or proportional odds models, depending on the distribution of the adherence measure, to explore associations of participant characteristics with poor adherence.

B) Additional analyses to examine the feasibility of teaching women to perform intervention-specific techniques:

Additional descriptive statistics may examine participants' self-efficacy and observed competence in performing intervention techniques during the mid-point of intervention programs (4 weeks). Within the yoga arm, investigators may examine participants' average self-efficacy in perform yoga postures at 4 weeks. Investigators may also examine average posture competency ratings based on the study yoga expert consultant's observations at 4 weeks. Similar analyses may be conducted for the physical conditioning group.

Within the yoga intervention arm, additional analyses may be conducted to examine participants' self-efficacy and observed competence in performing each individual yoga posture, to identify specific components of the yoga program that may post special challenges for the target population. Within the physical conditioning intervention arm, similar additional analyses may be conducted to examine participant's self-efficacy and observed competence in performing each physical conditioning exercise. These analyses will focus on 8-week data, although additional exploratory analyses may examine participants' self-efficacy and observed competence in performing intervention techniques mid-way through the intervention programs at 4 weeks.

C) Additional analyses to examine the completeness/quality of follow-up outcomes data:

Additional analyses may be performed to assess the completeness and quality of data obtained from pain logs and pain-related outcome questionnaires at the 8-week post-intervention timepoint. This includes the percentage of completed 7-day pain severity/intensity, interference, and impact measures returned at the 8-week post-intervention timepoint.

Additional analyses may examine the percentage of other expected pain-related outcome measures that are returned at 8 weeks or 8-weeks post-intervention. These include pain self-efficacy or fear-avoidance questionnaires, anxiety and depression symptom questionnaires, and sleep disturbance questionnaires. For all of the above, analyses will focus on the combined available sample of participants at the relevant timepoint, although further exploratory group-specific analyses may also be performed.

The study team may also examine the distribution of data from all of the above pain-related outcome measures at baseline, 8 weeks, and 8 weeks post-intervention, and calculate their standard deviations (SDs) and within-subject and within-site intraclass correlations (ICCs). These exploratory analyses may alert the investigative team to the need for transformation and ceiling/floor effects as well as guide decisions about the inclusion of measures in a future full-scale trial.

In recognition of potentially important differences in data completion, quality, or distribution, the investigative team may also pursue a limited set of analyses stratified by clinical recruitment site (i.e., San Francisco, Oakland, and Palo Alto, each of which will be the focus of a different intervention wave). This may alert investigators to gross variation or clustering across sites which could complicate a future multisite trial.

